7.10.1.1. Pre-Trialing Events

Because only device-, therapy-, or procedure-related adverse events and device deficiencies are being collected, it is unlikely that any adverse events will be reported prior to trialing. However, if any adverse events have an onset date on or after enrollment and prior to the Device Trial (Day 0) Visit, they will be summarized as Pre-Trialing Events. The denominator for percent of subjects who experienced the event will be all subjects in the Enrolled Analysis Set.

7.10.1.2. Trialing Events

Events that have an onset date on or after the Device Trial (Day 0) Visit and either through the Study Exit date or prior to the Implant Visit (whichever date is earlier) will be summarized as Trialing Events. The denominator for percent of subjects who experienced the event will be all subjects in the Tried Analysis Set.

7.10.1.3. Post-Implant Events

Events that have an onset date on or after the Implant Visit and prior to the Device Activation Visit will be summarized as Post-Implant Events. The denominator for percent of subjects who experienced the event will be all subjects in the Implanted Analysis Set.

7.10.1.4. Post-Device Activation Events

Events that have an onset date on or after the Device Activation Visit will be summarized as Post-Device Activation Events. The denominator for percent of subjects who experienced the event will be all subjects in the Treated Analysis Set.

In addition to overall Post Device-Activation event summaries, the subset of events with an onset date prior to the Month 3 Visit will be summarized.

For the purposes of reporting on ClinicalTrials.gov, the following summary tables of Post-Device Activation adverse events will also be created for subjects in the Treated Analysis Set:

- (1) All serious adverse events, summarized by MedDRA PT, sorted in descending order by percent of subjects with serious events, number of serious events, and then alphabetically by PT
- (2) All non-serious adverse events that occurred in at least 5% of subjects, summarized by MedDRA PT, sorted in descending order by percent of subjects, number of events, and then alphabetically by PT.

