## 11.6. Non-Reportable Events

Events that are not reportable for this study are:

- Lack of pain relief
  - Pain symptoms will be collected as part of the efficacy measures
- Sensation of stimulation (paresthesia)
  - Sensation of stimulation (e.g. tingling, buzzing) will not be reported as this may occur as part of this therapy. **Exception: Sensation or stimulation events that are uncomfortable to the subject (e.g. shocking, jolting) will be reported.**
- Adverse events unrelated to
  - Implanted SCS system, accessories or surgical procedure
  - Spinal cord stimulation therapy

Table 6 provides a list of common expected surgical adverse events. An expected surgical event will not be considered reportable unless it worsens or is present outside the stated timeframe post-procedure.

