**Table 6: Expected Surgical Adverse Events and Durations**

Event description	Time frame after the surgical procedure
Anesthesia-related nausea/vomiting	24 hours
Mild to moderate pain at surgical site	7 days
Low-grade fever (<100°F or < 37.8°C)	48 hours
Mild to moderate bruising / ecchymosis	7 days
Pocket site / incisional pain	14 days
Seroma	72 hours
Sleep problems (insomnia)	72 hours

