4.2. Safety Assessment

This study will characterize all device-, therapy-, or procedure-related adverse events and device deficiencies from enrollment to study exit.

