7.1.3. Analysis Sets

There will be 4 population sets for the purposes of analysis in this study.

Enrolled Analysis Set: All consented subjects.

Trialed Analysis Set: All subjects who have a Device Trial Day 0 Visit.

Implanted Analysis Set: All subjects who have a positive device trial with HD parameters at T9/T10 and are implanted with a neurostimulation system.

Treated Analysis Set: All subjects in the Implanted Analysis Set whose devices are activated at the Device Activation Visit.

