7.10. Safety Evaluation

7.10.1. Adverse Events and Device Deficiencies

In this study, only device-, therapy- and procedure-related adverse events (AEs) and device deficiencies that occur from enrollment through subject discontinuation from the study will be collected. All AEs and device deficiencies will be summarized.

Adverse events and device deficiencies will be summarized by study phase (e.g., Pre-Trialing, Trialing, Implant), with the appropriate number of corresponding subjects as the denominator within each study phase as described below.

Adverse events and device deficiencies, referred to as “events” within this section, will be summarized separately. Events will be coded and summarized using the Medical Dictionary for Regulatory Affairs (MedDRA). Summaries will be presented as the number of events, the number of serious events (for adverse events only), the number of subjects who experienced the event, and the percent of subjects who experienced the event.

Each event summary will be presented in 2 ways (separate tables) using MedDRA’s coding system:

- (1) By MedDRA System Organ Class (SOC) and Preferred Term (PT), sorted first by the recommended SOC order, then in descending order within PT by percent of subjects, number of events, number of serious events (for adverse events), and then alphabetically by PT

- (2) By MedDRA PT, sorted in descending order by percent of subjects, number of events, number of serious events (for adverse events), and then alphabetically by PT.

Each adverse event is evaluated for whether it qualifies as an Unanticipated Serious Adverse Device Effect (USADE). All USADEs will also be summarized separately by study phase as described below. If no USADEs occur, a statement indicating that will be included.

In addition to the summaries above, device deficiencies may also be summarized by device type and PT. Detailed listings of all adverse events and device deficiencies will be included in the final study report.

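### The only tables the visible SAP specifies for ClinicalTrials.gov start at device activation, so earlier related events, including serious ones, are not in them

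*SAP*

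**What the plan says.** SAP 4.2 sets the safety scope: "This study will characterize all device-, therapy-, or procedure-related adverse events and device deficiencies from enrollment to study exit". SAP 7.10.1 divides events by onset date into four phases, each summarized "with the appropriate number of corresponding subjects as the denominator within each study phase as described below". The Trialing phase takes "Events that have an onset date on or after the Device Trial (Day 0) Visit", up to study exit or the implant visit. The Post-Implant phase takes "Events that have an onset date on or after the Implant Visit and prior to the Device Activation Visit". The last phase starts on the day of the Device Activation Visit.

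Only that last phase (SAP 7.10.1.4) mentions the registry: "reporting on ClinicalTrials.gov, the following summary tables of Post-Device Activation adverse events will also be created for subjects in the Treated Analysis Set". Two tables follow, both by preferred term: all serious events, and non-serious events reaching 5% of subjects. SAP 7.1.3 defines the Treated Analysis Set as "All subjects in the Implanted Analysis Set whose devices are activated at the Device Activation Visit".

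Protocol 4.3 and 14.1 say that the study will be posted on ClinicalTrials.gov but do not say which safety tables will be used.

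**The concern.** Both planned surgical steps, trial lead placement and permanent implant, come before activation. Protocol 10.1.1 names spinal fluid leak, bleeding, infection and paralysis among the risks of implanting the system. Protocol 11.1 makes procedure-related events one of its three relatedness categories. Protocol 7.5 starts exposure at the device trial, and SAP 7.7 quantifies exposure separately for the Trialed, Implanted and Treated sets.

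If the posting follows the two specified tables, a registry reader would not see such an event, however serious, when it began before activation or occurred in a subject who was never activated. The public safety display would then be narrower than the study's stated safety scope, with nothing in the visible text to tell the reader so.

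**Working it through.** The plan states no figure on this point, so the check is a comparison of definitions followed by the length of the omitted interval.

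**Step 1. Registry coverage by phase.**

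| Phase | SAP section | Denominator | Registry table named |
|---|---|---|---|
| Pre-Trialing | 7.10.1.1 | Enrolled set | none |
| Trialing | 7.10.1.2 | Trialed set | none |
| Post-Implant, before activation | 7.10.1.3 | Implanted set | none |
| Post-Device Activation | 7.10.1.4 | Treated set | two |

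An event with onset before the Device Activation Visit cannot enter either registry table, whatever its seriousness. An event with onset on the activation day can.

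**Step 2. Subjects who cannot appear at all.**
- Subjects without sufficient relief on the HD settings in the device trial, who are exited (Synopsis, Device Trial Day 6) after a percutaneous lead procedure.
- Subjects who leave between implant and activation. SAP 7.7 provides for this by substituting the exit date when it computes exposure.

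SAP 7.10.2 also foresees system modifications between implant and activation.

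**Step 3. Length of the omitted interval from trial Day 0.** The inputs are the windows in Protocol Table 2.
- Trial Day 0 to a successful trial: at least 2 days (Day 2 Visit) and at most 4 + 4 = 8 days (Day 2 Visit at day 4, then Day 4 Visit 4 days later). Subjects who go on to the Day 6 Visit are exited, so 8 days is the longest trial that leads to implant.
- End of trial to implant: at most 30 days. Table 2 gives no lower limit, so 0 is assumed for the minimum.
- Implant to activation: 9 to 16 days, pending wound healing.

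Minimum: 2 + 0 + 9 = 11 days. Maximum: 8 + 30 + 16 = 54 days.

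Protocol 9.5 reschedules activation if the wound has not healed, so the interval can exceed 54 days, and it lengthens in subjects with slow wound healing. The time from baseline to trial Day 0, up to 14 days, also lies outside the registry tables, although SAP 7.10.1.1 considers events there unlikely.

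**Step 4. What the final study report shows.** Under SAP 7.10.1, adverse event summaries by phase include the number of serious events, unanticipated serious device effects are summarized by phase, and all events are listed. The difference between the report and the registry is therefore one of table specification, not of data collection.

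**The case against.** The strongest reply is that no text is breached. SAP 4.2 says what the study will characterize, not what the registry must show, and the final study report meets it. SAP Section 3 describes the SAP as covering the analyses for that report, so registry output is peripheral. Section 7.10.1.4 says the tables will be created in addition to others and does not bar posting more. Protocol 13.1.6 (Reports) and parts of the SAP are redacted and may hold further tables or a reason. All of this stands. It limits the point to the registry tables, and it means that a reader should not infer that earlier serious events will be withheld.

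There is also a plausible rationale. Protocol 8.2 classes subjects who fail the device trial as screen fails, and the Synopsis (Statistics) restricts the primary and secondary endpoints to implanted and activated subjects. A Treated-set table matches that population. However, the visible text does not give this as the reason, and it does not account for subjects implanted but not activated, or for earlier events in subjects who are later treated.

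Two stronger readings are tempting and are not supported.
- Protocol 11.6 says "An expected surgical event will not be considered reportable unless it worsens or is present outside the stated timeframe post-procedure", and Table 6 lists items such as "Pocket site / incisional pain". A reader might infer that what is collected before activation is mainly serious, worsened or prolonged. Table 6 removes only seven common surgical events. Uncomfortable stimulation is expressly reportable under 11.6, and Protocol 10.1.2 lists other risks that are not in Table 6, such as lead migration.
- A reader might take 215 − 100 = 115 subjects as the number left out. But 215 counts consented subjects, some of whom may never have a lead placed, and 100 is the minimum intended to reach 3 months, not the number treated.

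**Conclusion.** The point holds for the registry tables in the visible SAP. Followed as written, they omit every related event with onset before activation, including serious ones, and every event in subjects never activated. The omitted span is 11 to 54 days from trial Day 0 under the stated windows, assuming that implant may follow the end of the trial on the same day and that activation is not rescheduled. This measures time only. The documents give no event rates and no number of subjects trialed or implanted without activation, so the share of events or risk cannot be stated.

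No efficacy result, safety objective or study conclusion is affected, because the final study report covers all phases. The consequence for the public display is conditional on the posting following these tables and on the redacted text adding nothing. No outside registry rule is relied on. The change is worth making because the public safety result would otherwise be incomplete and the remedy is small.

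**What to change.** In SAP 7.10.1.4, keep the two post-activation tables unchanged and add for registry reporting:

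- a table of all serious adverse events in the Trialing phase, with the Trialed set as denominator (window as in 7.10.1.2);
- a table of all serious adverse events in the Post-Implant phase, with the Implanted set as denominator (window as in 7.10.1.3);
- any serious Pre-Trialing event, if one occurs;
- optionally, non-serious events at the 5% threshold within each phase.

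Do not merge everything into one Trialed-set table, because the larger denominator can hide a post-activation event. With assumed denominators, 6 of 100 treated is 6% and is shown, while 6 of 150 trialed is 4% and is not. The phase approach has its own limit: a non-serious event in 3 of 100 subjects in each of two phases is 3% in both and is shown in neither.

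If the sponsor keeps the restriction, the minimum is to give the reason in the SAP and to say in the registry entry that events with onset before activation are not shown.

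The cost is about one paragraph of SAP text. Phase windows, denominators and serious-event counts are already planned, so no new data are needed. The downside is slightly more output and higher displayed event counts.

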7.10.2. Surgical Revisions

System modifications following permanent system implant will be presented. Device modifications that occur between system implant and device activation will be summarized separately from the device modifications that occur after device activation. Summaries will include the device component(s) modified, the type of modification (explant, replacement, repositioning), and the primary reason for modification (adverse event, device deficiency, other). The percent of subjects with at least 1 device surgical revision will be summarized.

7.11.Changes to Planned Analysis

Any deviations from this SAP will be described and justified in the final study report, as appropriate.

8. Validation Requirements

Statistical programming code that affects the result of the main analysis (e.g., not including sensitivity or supporting analyses) for the primary objective shall be validated using Level I validation. Programming code that affects the result of the main analysis for the secondary objectives shall be validated at least using Level II validation. In addition, those main statistical analyses that are planned for publication and have not been previously validated should be validated with at least Level II validation. Level III validation may be used for any previously validated program where only minor/administrative changes were made (eg, change the location of the data directory). Additional measures may need to be validated as determined by statistical management.

9. References

[Redacted]

[Redacted]

[Redacted]

[Redacted content]

[Redacted text block]

[Redacted text block]

[Redacted text block]

[Redacted text block]

[Redacted text block]

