### 13.1.3. Interim efficacy analyses

An interim analysis providing preliminary characterization of the secondary objectives will be performed in late 2018 with the intent of presenting the results in early 2019. The details of these analyses will be specified in the SAP.

Analyses of the efficacy outcomes and safety assessment will be performed after 100 subjects have reached the 3-Month Visit, as described in section 13.1.6. The primary efficacy objective will not be evaluated. These analyses will be specified in the SAP and are not intended to be used to modify the study.

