### 13.6. Safety Assessment

All device-, therapy-, or procedure-related adverse events and device deficiencies from enrollment to study exit will be summarized. Adverse events and device deficiencies will be coded and summarized using the Medical Dictionary for Regulatory Affairs (MedDRA). Summaries will be presented as the number of events, the number of subjects who experienced the event, and the percent of subjects who experienced the event. Adverse events and device deficiencies will be summarized by study phase (e.g., Baseline, Trialing, Implant), with the appropriate number of corresponding subjects as the denominator within each study phase.

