7.7. Treatment Characteristics

Device exposure will be quantified and summarized separately for the Trialed, Implanted, and Treated Analysis Sets. Amount of exposure will be summarized using descriptive statistics such as mean, standard deviation, sum, minimum, and maximum.

For all subjects in the Trialed Analysis Set, the number of days of device exposure will be calculated as:

$$\text{Date of trialing leads explant} - \text{Date of Trialing Day 0}$$

If the date of trialing leads explant is unavailable, and the subject discontinues from the study during the trial, study exit date will be used in place of the trialing leads explant date.

For all subjects in the Implanted Analysis Set, the number of days of device exposure between implant and device activation will be calculated as:

$$\text{Date of Device Activation Visit} - \text{Date of Implant Visit}$$

If a subject discontinues from the study after implant prior to the Device Activation Visit, the study exit date will be used in place of the Device Activation Visit date.

Months of device exposure for subjects in the Treated Analysis Set will be calculated as:

$$[(\text{Cut-Off Date} - \text{Date of Device Activation Visit})/365.25]*12$$

Where Cut-off Date for each subject is, in order of priority:

- (1) the date of permanent system explant, if applicable, or
- (2) the date of study exit, or
- (3) the most recent follow-up visit (scheduled or unscheduled).

Programming data from the Neuro Programmer Upload (NPU) database will be evaluated for subjects in the Treated Analysis Set to determine whether subjects ever received physician preference stimulation settings (ie, non-HD settings) during the study. For subjects who received physician preference stimulation settings, the months from Device Activation to first use of physician preference stimulation settings will be quantified.

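### Post-activation adverse events and surgical revisions are reported as counts and crude percentages that ignore follow-up time, and the revision percentage has no stated denominator or time horizon

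*SAP*

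**What the plan says.** SAP 7.10.1 defines the content of the safety tables: "Summaries will be presented as the number of events, the number of serious events (for adverse events only"), followed by the number and percent of subjects affected. Protocol 13.6 plans the same kind of summary by study phase, "with the appropriate number of corresponding subjects as the denominator within each study phase".

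The SAP then fixes the denominators by phase. Between implant and activation: "The denominator for percent of subjects who experienced the event will be all subjects in the Implanted Analysis Set". After activation: "The denominator for percent of subjects who experienced the event will be all subjects in the Treated Analysis Set". Section 7.10.1.4 adds a shorter window, in which "the subset of events with an onset date prior to the Month 3 Visit will be summarized", but gives it no denominator of its own.

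For revisions, SAP 7.10.2 separates modifications before activation from those after it and describes component, type and reason. It closes with: "The percent of subjects with at least 1 device surgical revision will be summarized". It does not say percent of whom, or by when.

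SAP 7.7 derives months of exposure for each treated subject. The cut-off is explant, then study exit, then "the most recent follow-up visit (scheduled or unscheduled"). Exposure is summarised, including its total, but the visible text never combines it with events.

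Protocol 13.1.3 also schedules an earlier look: "Analyses of the efficacy outcomes and safety assessment will be performed after 100 subjects have reached the 3-Month Visit". It refers to section 13.1.6, which is redacted. The visible part of SAP 7.8 does not name safety, and the rest is redacted.

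**The concern.** Characterising safety is a stated aim of the study (Protocol 5.1.2, SAP 4.2). Adverse events are collected only until a subject discontinues. A subject who leaves at month 4 without an event stays in the denominator for the whole post-activation phase, as if known to be event-free to month 12. Events never observed can only add to the count, so a crude percentage cannot exceed the percentage that full 12-month follow-up of the same set would have shown, and will usually be lower.

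SAP 7.4, whose title covers dropouts, gives an imputation rule for pain scores but none for safety outcomes. The ingredients for a follow-up-adjusted figure are already derived in SAP 7.7 and are not used. A reader who takes the reported percentage as a 3-month or 12-month risk would find the device somewhat safer than the data support. For revisions, the reader cannot tell which risk is being estimated.

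**Working it through.** **The plan's own figures.** The visible text gives no event rate, attrition rate or safety precision, so there is no safety figure to reproduce. The efficacy design figures do reproduce (26 subjects for the primary test; Wilson half-width 9.6% at 100 subjects), but they have no bearing here.

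**Inputs from the documents**
- Planned follow-up is 12 months after activation for every treated subject (Protocol 6).
- Event collection ends at discontinuation (SAP 7.10.1).
- The study lasts about 3–4 years, with up to 15 months per subject (Protocol 6.1). Enrolment therefore takes about 36 − 15 = 21 to 48 − 15 = 33 months. For 100 treated subjects that is 100/33 = 3.0 to 100/21 = 4.8 activations a month.

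**Assumptions**
- The true 12-month risk is p = 10%.
- The proportion withdrawing by 12 months is d = 5–30%, independent of events.
- Activation is uniform over time.
- The hazard is constant or, as a check, front-loaded (Weibull shape 0.5).

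**Final report, constant hazard.** Take 12 months as the time unit, with λ = −ln(1 − p) and δ = −ln(1 − d). The expected crude proportion is

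C = λ/(λ + δ) × [1 − exp(−(λ + δ))].

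For d = 15%: λ = 0.1054, δ = 0.1625, sum 0.2679. C = 0.3933 × 0.2350 = 9.24%.

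| Dropout by 12 months | Crude, constant hazard | Crude, front-loaded |
|---|---|---|
| 5% | 9.75% | 9.84% |
| 10% | 9.50% | 9.67% |
| 15% | 9.24% | not run |
| 20% | 8.98% | 9.32% |
| 30% | 8.44% | 8.96% |

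**Early safety analysis, if the whole Treated set is the denominator.** Let follow-up at the cut be uniform on 0 to A months, capped at 12, with 15% dropout and a constant hazard. Subjects with 12 months possible contribute 9.24%. Those still under 12 months contribute on average

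0.3933 × [1 − 0.2350/0.2679] = 4.83%.

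The crude percentage is then (A − 12)/A × 9.24 + 12/A × 4.83:
- A = 24: 0.500 × 9.24 + 0.500 × 4.83 = 7.0%
- A = 33: 0.636 × 9.24 + 0.364 × 4.83 = 7.6%

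Without dropout, at 5 and 3 activations a month, the crude figures are 7.4% and 8.4% (constant hazard) or 8.3% and 8.9% (front-loaded).

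**Pre-Month-3 subset at the same cut.** With r activations a month, 100 + 3r subjects are treated and 3r have under 3 months. Under a constant hazard those 3r carry on average about half the 3-month risk. The ratio of crude to true is about (100 + 1.5r)/(100 + 3r):
- r = 3: 104.5/109 = 0.96
- r = 5: 107.5/115 = 0.93 to 0.94

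Front-loaded, the ratios are 0.97 and 0.96. If activation stopped at about 100 subjects, few or none would have under 3 months at the cut, and the shortfall in this window would come mainly from dropout.

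**The case against.** Several points on the other side are sound.

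- **The plan offers more than percentages.** Event counts, serious-event counts, a split by phase, a pre-Month-3 subset, full listings and total exposure are all planned. A reader could form a rough rate. This stands, but no such rate is pre-specified, and the Month 3 cut is tied to a visit, so it is undefined for a subject who has none.
- **Follow-up is planned to be equal.** Everyone treated is due 12 months, there is no comparator arm, and a gap of 0.8 points at 15% dropout is small beside a Wilson 95% interval of about 5.5–17.4% for 10 events in 100. Subjects who leave because of an adverse event already count as events. This stands for the final report.
- **The plan does not call its percentages 12-month risks.** True, but for revisions it names no horizon at all.

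Stronger readings are tempting and should be resisted.

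- A reader might infer that the 100-subject analysis will definitely divide by everyone treated. The documents do not show this. Protocol 13.1.6 and part of SAP 7.8 are redacted, SAP 7.10 is written for the final report, and a denominator restricted to subjects with 3 months cannot be ruled out.
- A reader might infer that revisions are divided by a whole analysis set. SAP 7.10.2 gives no denominator, and that omission is the defect.
- A reader might suppose rapid accrual, with activation packed into 9 to 12 months, and conclude that the early percentage is less than half the true 12-month risk. The stated study duration does not fit that pace.

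**Conclusion.** The point holds in a limited form. The visible plan contains no follow-up-adjusted estimate for adverse events or revisions, and the revision percentage lacks a denominator and a horizon. The direction of the error is known: it understates risk.

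The size is modest in the final report, about 2–5% relative at 5–10% dropout and up to about 16% relative at 30% (10% shown as 8.4%). At the early safety analysis a true 12-month risk of 10% could appear as about 7.0–7.6%, conditional on a whole-set denominator and on the figure being read as 12-month risk. For the pre-Month-3 window the shortfall is only a few percent relative at 3–5 activations a month.

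All magnitudes rest on assumed event, dropout and activation rates and on independent withdrawal. Events concentrated soon after activation would shrink them. The tabulation used at the early analysis cannot be confirmed from the public text.

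**What to change.** 1. In SAP 7.10.2, state the denominator for the revision percentage: the Implanted Analysis Set before activation and the Treated Analysis Set after it.
2. In SAP 7.10.1.4 and 7.10.2, add cumulative incidence with 95% confidence intervals and numbers at risk at 3 and 12 months after activation, for first surgical revision, first related adverse event and first related serious adverse event. Censor at study exit or last contact. Treat death as a competing event. Treat explant as competing for adverse events but as an event for revisions. Plain Kaplan-Meier without these rules can overstate incidence.
3. Give events per subject-time, using the exposure already defined in SAP 7.7.
4. Apply the same to any early safety report.
5. Keep the crude counts and percentages as description.

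The cost is SAP wording and a little programming on dates already collected, with no change to study conduct. The downside is a few more tables and slightly less favourable figures.
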